Investigation of different relaxation interventions on physical and psychological changes in breastfeeding mothers in China: A pilot study

[name] ¹

[name] ¹

From: ¹ The Childhood Nutrition Research Centre, Institute of Child Health, University College London.

Principal Investigator: [name], Institute of Child Health, University College London.
[name]
Email: [contact]

1. Introduction and Rational

Breastfeeding is of great importance for infant health and development [1]. Accumulated evidence show the effects of human breast milk on optimizing infant growth of brain and body, as well as protecting against infection and developing the immune system [1-4]. In a recent *Lancet* review [2], which summarised the findings of 28 systematic reviews and meta-analyses, the psychological and cognitive benefit of human breast milk for infants are emphasised. Moreover, the protective effects of breastfeeding on reducing the risk of obesity, type 2 diabetes, cardiovascular disease, and allergic disorders such as asthma are identified for infants later in life. Apart from the health benefits on infants, breastfeeding could also provide mothers with a better postpartum recovery [1, 2], and associated with decreased risk of osteoporosis, cardiovascular diseases, diabetes, and ovarian and breast cancer in their later life [2, 5-8]. However, despite a number of health programmes designed to promote breastfeeding, it is widely recognised that the exclusive breastfeeding (EBF) rates in many countries are disappointingly low and resistant to change [2]. Overall, less than half of the world population exclusively breastfeed their infants up to six months, with a global rate of 39% reported by UNICEF (2012) [9]. Apart from the socio-economic and cultural factors which may influence mother's decision on breastfeeding, lactation performance is also influenced by maternal physiological and psychological condition [10].

Stress can be one of the factors that influence the successful breastfeeding [11]. Accumulated evidence show that stress can influence the stress-related hypothalamic-pituitary-adrenal (HPA) axis thereby affect the lactation. A number of studies reported the effectiveness of relaxation techniques on reducing stress and anxiety, which were associated with improved endothelial function [12, 13]. In a previous MOM study, maternal psychological state was manipulated using relaxation therapy in 58 Malaysian mothers breastfeeding their full-term infant. The therapy show significant effects in reducing maternal stress during lactation, favourably affecting breast milk composition (higher fat/energy and higher total carbohydrate) and positively influencing infant sleeping behaviour and growth.

However, there are lack of studies evaluating the effectiveness among different relaxation techniques. There are many relaxation methods, including relaxation training [14], guided imagery [12], music

therapy [15], yoga and progressive muscle relaxation (PMR) [16]. Most of these use the cognitive and/or behavioural relaxation approach which emphasizes the development of a relaxation response to counteract the stress response of anxiety [17]. The relaxation response refers to a set of integrated physiological mechanisms and 'adjustments' that are elicited when a subject engages in a repetitive mental or physical activity and passively ignores distracting thoughts [17].

Light therapy is another technique which may be used to promote relaxation. Evidence shows that light could stimulate the suprachiasmatic nucleus (SCN) located in the hypothalamus on top of the optic chiasm and influence the secretion of cortisol and adrenocorticotropic hormone by mediating the HPA axis [18]. Research also indicates that light may induce gene expression ("circadian clock" - related or "sleep"-related genes in depression) in the adrenal gland via the SCN-sympathetic nervous system [19]. An increasing number of studies reported the application of light therapy for the treatment of a range of mental disease, namely seasonal affective disorder (SAD) [20], non-seasonal depression [21], total sleep deprivation [22], and antepartum depression [23]. Studies also show that exposure to blue light is associated with reduced heart rate and blood pressure [24], while improved resting metabolic rate was observed in patients with SAD following exposure to bright light [25].

This pilot study aims to find the most effective relaxation technique to help mothers who are firstly breastfeeding their infant. Hence, we will evaluate the effects of five different relaxation techniques on physical and psychological changes in Chinese mothers who are firstly breastfeeding their infant. The ultimate aim of this study is to select the most appropriate therapies for breastfeeding mothers to be used in a subsequent trial investigating the impact of relaxation theory on breastfeeding outcomes in mothers who deliver a late preterm infant. Five types of intervention used in this study include: guided relaxation meditation tape, music tape, relaxation lighting, combined relaxation meditation and lighting, and combined music and lighting.

2. Objectives

To compare and evaluate the impact of five relaxation interventions on changes of heart rate (HR), blood pressure (BP), fingertip temperature (FT) and level of relaxation among Chinese breastfeeding women. Additionally, participants' perceptions and feelings about each relaxation technique will also be evaluated.

3. Hypotheses

Primary: Compared to the control state, all five relaxation interventions associated with increased perceived relaxation in varying degrees and reduced perceived stress.

Secondary: The two combination treatments (guided relaxation tape with relaxation lighting, and music tape with relaxation lighting) might show more effectiveness than other three treatments.

4. Study Design

The present study will be conducted at Beijing Children Hospital, Beijing, China. A within-subject design will be used to evaluate the effectiveness and participants' feeling towards the five tested interventions compared to a control situation.

4.1 Population and recruitment

The study population will be Chinese women who are currently breastfeeding their infants. Recruitment will be take place through social media and community flyers in Beijing Children Hospital. After obtaining approval. Advertisements will be posted in the hospital while flyers will be sent to local communities. Interested women can contact us by email. Details about the study will be explained in the information sheet. After checking the eligibility and obtaining written informed consent, all eligible participants will be enrolled in the study.

4.2 Sample size calculation

To estimate the sample size of this pilot study, standard formulas (21) used for calculation are:

$$\text{Sample size (per equal-sized group)} = 16 \times \text{standard deviation} \div (\text{difference})^2$$

Here the effect size and standard deviation (SD) are estimated from a previous research (22), which evaluated the effect of audio-visual imagery on patient anxiety and physiological parameters. A

sample of 51 patients was able to demonstrate a significant reduction in HR (mean change (Z) = -0.75, SD = 1.00; p=0.01). Accordingly, the estimated sample size (per equal-sized group) would be 28. However, since the present study will use a within-subject design, a sample of 14 participants will likely be able to demonstrate changes. Considering the potential drop-off rates, we intend to involve a total of 15-20 subjects in this study.

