4.3 Eligibility criteria

Inclusion Criteria	Exclusion Criteria
Women (primips) who are exclusively breast feeding their infants	Women who are breastfeeding their second infant and have previous experience of breastfeeding for their first infant
Between 1 month to 4 months after delivery and stay at home	After 3 months of delivery and back to the work place
Generally healthy	Women who have mastitis, or any condition that may affect breastfeeding, blood pressure, heart rate, energy expenditure, hearing ability or vision
18-45 years of age	Smokers
	Did not attend any other clinical trials within the latest 12 months

5. Study Procedures

After obtaining informed consent, all participants enrolled in this study will be asked to attend for 30 minutes once to three times per week for five relaxation treatments and one control (no treatment). The emotions and feelings of participants in both intervention and control treatment will be assessed before and after each treatment or control.

The duration of this study is six weeks. In order to fit with the subject's schedule and control the circadian rhythm, all treatments and control sessions will take place on different days each week. Each participant can choose a 30-minute time slot to fit their timetable. To make the outcome assessment more consistent, participants are encouraged to come at the same time of the day they chose. The order of interventions will be randomly assigned for each participant. Both relaxation interventions and control will be conducted in the breastfeeding room located at Beijing Children Hospital. This room is private, quiet and has comfy seating. Participants will be asked to leave their personal belongings, including any electronic devices, books and magazines, and personal work, during the experiment period.

6. Treatment of Subjects

A total of five interventions will be used in this study, in which, three basic interventions are: guided relaxation meditation tape, music tape, and relaxation lighting (Philips Hue). Moreover, since we hypothesise that a potential larger effect might be observed when using combined relaxation interventions to stimulate different senses (vision and audition) at the same time, we combined the guided relaxation tape with lighting and the music tape with lighting as two additional interventions in this study. All participants will receive all five treatments and control in random order.

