6.4. Guided relaxation tape with relaxation lighting and music with lighting

Previous research compared the effects of guided imagery (verbal protocol) and verbal protocol with background music (24) and found that participants using the verbal protocol with background music

reported lower relaxation compared to the verbal protocol only group. The authors proposed that this might be due to confusion during the intervention when both verbal sounds and background music were experienced by participants. Therefore, in this study, we aim to evaluate the effectiveness of guided relaxation meditation with relaxation lighting as well as the music therapy with relaxation lighting, to find out whether the combined treatment could increase the relaxation level by stimulating vision (lighting) and audition (tape) together. It can be hypothesised that the effects of this combination therapy might be enhanced since the light and sounds will affect the HPA axis through different pathways.

7. Outcome measurements

Primary outcomes of this study will be perceived relaxation level, HR, BP and FT, while the secondary outcomes will be the perceptions and feeling about each treatment, including general satisfaction, perceived effectiveness, and likelihood of wanting to use the intervention in future. Evaluation will base on the design and content of the relaxation technique.

The HR, BP and FT will be measured at both the start and the end of the experiment. An automatic BP machine will be used for the measurements of HR and BP. The BP will be measured three times and the mean of three will be calculated and recorded. A thermometer will be used for the FT measurement. For the evaluation of levels of relaxation and feelings of each intervention, a visual analogue scale will be employed at the beginning and end of each intervention.

8. Statistical Analysis

Data will be analysed using SPSS 24.0. Paired t-test will be used to detect changes in each of the primary outcomes before and after the treatment. One-way ANOVA will be conducted to find differences between control and each intervention group. Post-hoc analysis will be used to compare the effectiveness of each treatment. Differences will be considered statistically significant at $p<0.05$.

9. Ethical Consideration

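### Section 4.2 halves 28 to 14 on the within-subject design alone, without the correlation this needs, and section 8's one-way ANOVA drops the pairing that 14 relies on

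*Protocol*

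**What the plan says.** Section 4.2 of the protocol takes its effect size from an earlier study of audio-visual imagery, in which a "sample of 51 patients was able to demonstrate a significant reduction in HR (mean change (Z) = -0.75, SD = 1.00; p=0.01". It puts the difference of 0.75 and the SD of 1.00 into a formula for two equal groups and concludes that "the estimated sample size (per equal-sized group) would be 28". The next step is the only adjustment for the design: "since the present study will use a within-subject design, a sample of 14 participants will likely be able to demonstrate changes". Allowing for drop-off, at a rate it does not give, it then says "we intend to involve a total of 15-20 subjects in this study".

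Three other places bear on this:

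- Section 3, primary hypothesis: "Compared to the control state, all five relaxation interventions associated with increased perceived relaxation in varying degrees and reduced perceived stress". The reference is the control session, not the pre-session reading.
- Section 6: "All participants will receive all five treatments and control in random order". Each mother therefore contributes six sessions.
- Section 8: "Paired t-test will be used to detect changes in each of the primary outcomes before and after the treatment", and for the comparison with control, "One-way ANOVA will be conducted to find differences between control and each intervention group". No subject term or repeated-measures form is named.

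**The concern.** A within-subject design does not halve the two-group number by itself. What it saves depends on how strongly a mother's results in two sessions are correlated, or equivalently on the SD of her paired difference. With no correlation, about 28 mothers would still be needed, each serving in both conditions. Section 4.2 gives no correlation and does not say whether its SD of 1.00 is between persons or of a change within persons.

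The saving also exists only if the analysis uses the pairing. The paired t-test in section 8 pairs before with after within one session. The comparison with control, which is what the primary hypothesis is about, goes to a method that as named has no pairing.

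The pilot is meant to choose therapies for a subsequent trial. As written, a reader cannot tell what difference from control 14 mothers, or 15-20, could detect.

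**Working it through.** **Inputs.** Difference 0.75, SD 1.00, two-group size 28, within-subject size 14 and enrolment 15-20 are from section 4.2. The significance level 0.05 is from section 8. Assumed: two-sided testing; 80% power, which the constant 16 implies; a single comparison; and within-mother correlations (ρ) of 0.3, 0.5 and 0.7, since none is given.

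**1. The plan's own figures.** 16 × 1.00 / 0.75² = 16 / 0.5625 = 28.4, stated as 28. With unrounded normal quantiles, 2 × (1.960 + 0.842)² / 0.75² = 27.9. So 28 reproduces, and 14 is 28 / 2.

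**2. Intervention versus control, normal approximation.** The SD of the paired difference is 1.00 × √(2(1 − ρ)), so n = (1.960 + 0.842)² × 2(1 − ρ) / 0.75² = 27.9 × (1 − ρ). Setting n = 14 gives ρ = 1 − 14/27.9 = 0.50. At ρ = 0, n is 28.

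**3. The same comparison, exact paired t-test.** The standardised paired difference is dz = 0.75 / √(2(1 − ρ)); power is from the noncentral t distribution.

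| Assumed ρ | dz | Power, n=14 | Power, n=15 | Power, n=20 | n for 80% |
|---|---|---|---|---|---|
| 0.3 | 0.634 | 59% | 63% | 77% | 22 |
| 0.5 | 0.750 | 74% | 77% | 89% | 16 |
| 0.7 | 0.968 | 92% | 94% | 98% | 11 |

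In reverse, what must hold for 80% power (largest SD of the difference = 0.75/dz; lowest ρ = 1 − 0.75²/(2dz²)):

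| Completers | Detectable dz | Largest SD of the difference | Lowest ρ |
|---|---|---|---|
| 14 | 0.810 | 0.93 | 0.57 |
| 15 | 0.778 | 0.96 | 0.54 |
| 16 | 0.749 | 1.00 | 0.50 |
| 20 | 0.660 | 1.14 | 0.36 |

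**4. Before-after reading.** If 1.00 is the SD of a within-person change, n = 8 / 0.75² = 14.2 and no correlation between sessions is needed. Here dz = 0.750, so the ρ = 0.5 row of the first table applies: 74% power at 14, and 16 for 80%.

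**5. What the cited p-value suggests.** A paired change of 0.75 with SD 1.00 in 51 patients gives t = 0.75 × √51 = 5.36 on 50 degrees of freedom, p = 0.000002. Two groups of about 25.5 (an assumed equal split) give t = 0.75 / √(2/25.5) = 2.68, p = 0.010, which matches the stated value. This leans towards a between-person SD. It does not settle the matter, because the protocol does not say which test produced the p-value.

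**6. One-way ANOVA as named.** With 14 per condition, six conditions treated as independent and pooled variance on 6 × 13 = 78 degrees of freedom, a single contrast has standard error √(2/14) = 0.378. The observed difference must exceed about 1.99 × 0.378 = 0.75 SD to reach p<0.05, which is the planned difference itself, so power is about 50%. A two-sample t-test gives 48%. With 20 per condition the figures are 65% and 64%. If a mother's sessions are positively correlated, the true standard error of the contrast is smaller by the factor √(1 − ρ), so the one reported is too large.

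**The case against.** The strongest defence is that 14 has a coherent reading. Section 4.2 speaks of demonstrating changes and cites a mean change, and section 8 plans a paired t-test of before against after. On that reading 8/0.75² gives 14 with no correlation needed, and the gap between 74% and 80% is only the small-sample t correction. This stands in part: the arithmetic is not wrong, and 14 can be derived. But the protocol does not say that 1.00 is the SD of a change, and this reading leaves the comparison with control unsized.

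It is also fair that 14 is hedged, that enrolment is 15-20, and that this is a pilot. At a correlation of 0.5, 16 to 20 completers give 80-89%. Still, section 4.2 chose to justify its number by what it could demonstrate, so that justification should hold.

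On section 8, one-way ANOVA may be shorthand for a one-factor repeated-measures analysis, and an SAP not at hand might say so. The protocol text does not, and the method it names is at odds with its own design.

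A reader might infer more: that the study is shown to be underpowered, or that the table above gives power for the primary hypothesis. The documents support neither. A correlation of 0.57 or more would make 14 adequate. The 0.75 is a heart-rate effect from another study, assumed here to carry over to the comparison with control, whereas the primary hypothesis concerns perceived relaxation and stress.

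**Conclusion.** The point holds as an unsupported step plus a mismatched analysis. The move from 28 to 14 rests on a within-mother correlation, or an SD of the difference, that the protocol does not state. The number needed for 80% power runs from 11 to 22 over assumed correlations of 0.7 to 0.3, so neither 14 nor the planned 15-20 can be called adequate or inadequate from the document alone. Even on the reading kindest to the plan, 14 falls two short of the 16 needed.

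The ANOVA limb is firmer, because it concerns a method the protocol names. Taken as written it gives wrong standard errors for six sessions of the same mothers and forgoes the gain that 14 presupposes.

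All power figures assume two-sided 5%, one comparison, a standardised heart-rate difference of 0.75 and complete data.

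**What to change.** 1. In section 8, replace the one-way ANOVA with a repeated-measures analysis that has mother as a subject term, or with paired comparisons of each intervention with control.
2. In section 4.2, drop the claim based on halving. Say what SD 1.00 is the SD of, and which comparison is being sized.
3. Keep 15-20, and describe it by the standardised within-mother difference detectable with 80% power at two-sided 5% for a single comparison: about 0.78 with 15 completers and 0.66 with 20. State that a difference of 0.75 with an SD of the difference of 1.00 reaches 80% only with 16 or more completers.

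The cost is one rewritten paragraph, one rewritten sentence and a slightly less favourable stated figure. Enrolment does not change. The text should acknowledge that, for a difference of 0.75, the low end of 15-20 does not reach 80% unless the correlation is about 0.54 or more, and that at a correlation of 0.3 even 20 completers (77%) would not.

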4.3 Eligibility criteria

Inclusion Criteria	Exclusion Criteria
Women (primips) who are exclusively breast feeding their infants	Women who are breastfeeding their second infant and have previous experience of breastfeeding for their first infant
Between 1 month to 4 months after delivery and stay at home	After 3 months of delivery and back to the work place
Generally healthy	Women who have mastitis, or any condition that may affect breastfeeding, blood pressure, heart rate, energy expenditure, hearing ability or vision
18-45 years of age	Smokers
	Did not attend any other clinical trials within the latest 12 months

5. Study Procedures

After obtaining informed consent, all participants enrolled in this study will be asked to attend for 30 minutes once to three times per week for five relaxation treatments and one control (no treatment). The emotions and feelings of participants in both intervention and control treatment will be assessed before and after each treatment or control.

The duration of this study is six weeks. In order to fit with the subject's schedule and control the circadian rhythm, all treatments and control sessions will take place on different days each week. Each participant can choose a 30-minute time slot to fit their timetable. To make the outcome assessment more consistent, participants are encouraged to come at the same time of the day they chose. The order of interventions will be randomly assigned for each participant. Both relaxation interventions and control will be conducted in the breastfeeding room located at Beijing Children Hospital. This room is private, quiet and has comfy seating. Participants will be asked to leave their personal belongings, including any electronic devices, books and magazines, and personal work, during the experiment period.

6. Treatment of Subjects

A total of five interventions will be used in this study, in which, three basic interventions are: guided relaxation meditation tape, music tape, and relaxation lighting (Philips Hue). Moreover, since we hypothesise that a potential larger effect might be observed when using combined relaxation interventions to stimulate different senses (vision and audition) at the same time, we combined the guided relaxation tape with lighting and the music tape with lighting as two additional interventions in this study. All participants will receive all five treatments and control in random order.

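### Session order is randomised for each woman with no stated counterbalancing; a Williams square would recover a modest loss of precision at almost no cost

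*Protocol*

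**What the plan says.** Section 5 (Study Procedures) states: "The order of interventions will be randomly assigned for each participant". Section 6 (Treatment of Subjects) repeats it: "All participants will receive all five treatments and control in random order". Neither section mentions a Latin or Williams square, a list of sequences, blocking or any other counterbalancing.

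The other relevant statements are:

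- **Size.** Section 4.2: "we intend to involve a total of 15-20 subjects in this study".
- **Spacing.** Section 5: "all treatments and control sessions will take place on different days each week". No minimum interval between sessions is given beyond that.
- **Measurement.** Section 5 says that feelings "will be assessed before and after each treatment or control". Section 7 has heart rate, blood pressure, fingertip temperature and the visual analogue scale taken at the start and the end.
- **Analysis.** Section 8 plans paired t-tests for before-to-after change and then: "One-way ANOVA will be conducted to find differences between control and each intervention group". It names no term for session, sequence or preceding condition.

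**The concern.** Each woman attends six sessions, and her response may change over them as she gets used to the room, the cuff and the scale, or becomes better at relaxing. The conditions also share components: the tape and the music are each used alone and again with lighting. A woman who has already heard the tape alone meets the combination with half of it familiar. Session number and preceding condition may therefore matter, particularly for the secondary hypothesis in Section 3, which sets the combinations against the single techniques.

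Free random orders balance these influences only on average over many trials. One realisation with fewer than 20 women can be noticeably uneven, and Section 8 names no model term that would adjust for it. The pilot is meant to guide the choice of therapy for a later trial (Section 1), so avoidable noise in the comparisons between conditions is worth removing if that costs nothing.

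**Working it through.** **Inputs.** Six conditions, so six sessions (Sections 5 and 6); N = 15-20 (Section 4.2); order random for each woman, read as an independent free draw. The within-woman SD of the before-to-after change is set to 1. The size of any drift over sessions is not in the Protocol and is assumed.

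**The plan's own figure.** Section 4.2 uses "mean change (Z) = -0.75, SD = 1.00; p=0.01": 16 × 1.00 / 0.75² = 28.4, stated as 28 per group and halved to 14. This reproduces, and the choice of order scheme does not alter it.

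**Does a balanced scheme exist?** Six is even, so one 6 x 6 Williams square suffices. In it each condition occurs once in every position and follows every other condition once. With 18 women (three per sequence) all of these counts equal 3.

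**Imbalance under free orders, N = 18.**

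- In one random order the variance of a position is (6² − 1)/12 = 35/12. The difference between two conditions' positions has variance 2 × (35/12) × (6/5) = 7. Averaged over 18 women, its SD is √(7/18) = 0.62 sessions. In 20,000 simulated draws the technique-control gap exceeded 0.5 sessions in 40% and 1.0 in 10%.
- The number of women with control first is Binomial(18, 1/6), with mean 3. P(≤ 1) + P(≥ 5) = 0.34.
- For one audio technique alone against the same audio with lighting, which comes first is Binomial(18, 1/2). A split of 12:6 or worse has probability 2 × 31180/262144 = 0.238. For at least one of the two such pairs it is 1 − (1 − 0.238)² = 0.42.

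**Simulated comparison.** There were 3,000 free designs per N, against Williams sequences allocated in random blocks of six. Variances are averages over 200 designs, relative to the ideal 2σ²/N, in a model with woman, session and condition, without and with first-order carry-over.

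| | N = 15 free / Williams | N = 18 free / Williams | N = 20 free / Williams |
|---|---|---|---|
| Mean span of the conditions' average session | 1.22 / 0.39 | 1.12 / 0 | 1.05 / 0.24 |
| Some ordered neighbour pair never occurs | 89% / 0% | 69% / 0% | 55% / 0% |
| Variance, session modelled | 1.077 / 1.008 | 1.062 / 1.000 | 1.055 / 1.004 |
| Variance, session and carry-over modelled | 1.221 / 1.053 | 1.177 / 1.036 | 1.161 / 1.044 |

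No free design was exactly balanced over sessions. At N = 18 the ratio of free to Williams is 1.062/1.000 = 1.06 with session modelled, and 1.177/1.036 = 1.14 with carry-over added.

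**If session is ignored.** Let the before-to-after change drift linearly by g within-woman SD from session 1 to session 6, that is g/5 per session. The chance error in a contrast has SD (g/5) × √(7/N) and mean zero. Relative to 2/N, the added variance is (g²/25) × 7/2 = 0.14g², whatever N is. At N = 18 the standard error is √(2/18) = 0.33:

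| Assumed g | Error SD | Added variance |
|---|---|---|
| 0.25 | 0.03 | 1% |
| 0.5 | 0.06 | 4% |
| 1.0 | 0.12 | 14% |

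Under three full Williams squares this linear drift cancels from every contrast.

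**The case against.** The strongest reply is that nothing here is invalid. A random order for each participant is an accepted crossover method, and its expected error from session effects is zero. That stands. A reader might infer that the comparisons are biased by order; the documents do not support this, because randomisation removes any systematic link between condition and session.

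A reader might also infer that order effects will change which technique looks best. That is not shown either. The Protocol gives no drift size, the chance error for the assumed drifts is small beside the standard error, and no ranking of the techniques was simulated.

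The design already has protections. Habituation that moves the before and after readings equally cancels in the change, so only drift in the change itself counts. Separate days, and the encouragement to keep the same time of day, limit carry-over. These points stand, although familiarity with a shared tape or piece of music, or learning to relax, can still act on the change. The 14% carry-over figure applies only if carry-over is modelled, which Section 8 does not plan.

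Finally, the wording does not exclude drawing each woman's order from a balanced list, and a SAP or randomisation plan might say more. That is fair as far as it goes. However, the natural reading is a free draw, the order scheme is part of the design, and Section 8 does name a between-condition analysis without session.

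**Conclusion.** The point holds as a minor one. The Protocol states random order without counterbalancing, and at this size free orders leave session position and preceding condition unbalanced by chance in practically every realisation. The consequence is a modest, avoidable loss of precision and robustness; the comparison remains valid. At N = 18 a technique-control contrast has about 6% more variance than under a Williams square with session modelled, and about 14% more with carry-over modelled as well. With session ignored it has about 1-14% more.

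These sizes assume independent free orders, six completed sessions per woman and a woman effect in the model. The last range also assumes linear drifts of 0.25-1.0 within-woman SD.

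**What to change.** Replace the order sentence in Section 5, and align Section 6, along these lines: participants will be randomly allocated, in blocks of six, to the six sequences of a 6 x 6 Williams square, with the conditions randomly assigned to its letters; the target is 18 women, three per sequence. In Section 8, include woman and session number in the between-condition model.

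The cost is a different randomisation list. The number of visits is unchanged, and 18 lies inside the planned 15-20. The session term uses five degrees of freedom: with 18 × 6 = 108 observations, the residual falls from 108 − 1 − 17 − 5 = 85 to 80. Balance is exact only if all 18 women complete. At 15, 16, 17, 19 or 20 women the counts differ by at most 1, and drop-outs make the balance approximate, but it stays much closer than under free random orders.
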